15.2 Adverse Events (Primary and Secondary Endpoints - Phase I)

Treatment emergent adverse events (TEAEs) are those events with onset dates occurring during the on-treatment period for the first time, or if the worsening of an event is during the on-treatment period as defined in Section 9.

TEAEs of grade ≥ 3 are a primary endpoint for the study. The analysis is described below in section 15.2.1. Secondary endpoints related to adverse events for this study include the following:

- Occurrence and severity of TEAEs (See section 15.2.1 for a description of the analysis.)
- AEs of special interest including immune-related adverse events and infusion related reactions (See section 15.3.3 for a description of the analysis)
- Study drug related adverse events. (See section 15.2.1 for a description of the analysis.)

All analyses described in Section 15.2 and 15.3 will be based on TEAEs if not otherwise specified. The AE listings will include all AEs (whether treatment-emergent or not). AEs outside the on-treatment period will be flagged in the listings.

The following categories of TEAEs are defined for reporting:

- **Related Adverse Events (secondary endpoint):** adverse events with relationship to study drug (as recorded on the AE eCRF page, Relationship with study drug = Related) reported by the investigator and those of unknown relationship (i.e. no answer to the question “Relationship with Avelumab”).
- **Serious Adverse Events (SAE):** serious adverse events (as recorded on the AE eCRF page, Serious Adverse Event = Yes).
- **Adverse Events Leading to Treatment Discontinuation:** adverse events leading to permanent discontinuation of study treatment (as recorded on the AE eCRF page, Action taken with study treatment = Drug withdrawn).
- **Adverse Events Leading to Death:** adverse event leading to death (as recorded on the AE eCRF page, Outcome = Fatal, as well as AEs of Grade 5).
- **TEAEs of Special Interest (secondary endpoint)**
 - **Immune Related Adverse Events (irAE):** For SMC meetings, potential irAEs will be identified according to a pre-specified search list of MedDRA PTs, documented in a version-controlled repository maintained by the Sponsor. For the final analysis, immune related adverse events according to case definition classified by medical review. Details are included in Table 10 in Appendix I.
 - **Infusion Related Reactions (IRR):** IRRs are identified based on a list of MedDRA PTs. The detailed criteria of the timing relationship to infusion are specified in Table 11 in Appendix I.

Unless otherwise specified, AEs will be summarized by number and percentage of subjects with the AE in the category of interest as described above by dose level, primary system organ class (SOC) and preferred term (PT) in decreasing frequency for the total column.

Each subject will be counted only once within each SOC or PT. If a subject experiences more than one AE within a SOC or PT for the same summary period, only the AE with the strongest relationship or the worst severity, as appropriate, will be included in the summaries of relationship and severity.

15.2.1 All Adverse Events

Adverse events will be summarized by worst severity (according to NCI-CTCAE version 4.03) per subject, using the latest version of MedDRA PT as event category and MedDRA primary SOC body term as Body System category.

In case a subject has events with missing and non-missing grades, the maximum of the non-missing grades will be displayed. No imputation of missing grades will be performed.

The following tables will be created:

- The overall summary of AEs table will include the frequency (number and percentage) of subjects with each of the following by dose level:
 - TEAEs
 - Related TEAEs
 - Serious TEAEs
 - Related Serious TEAEs
 - TEAEs, Grade ≥ 3 (primary endpoint)
 - Related TEAEs, Grade ≥ 3
 - TEAEs leading to permanent treatment discontinuation
 - Related TEAEs leading to permanent treatment discontinuation
 - TEAEs leading to death
 - Related TEAEs leading to death
 - Treatment-emergent irAEs
 - Treatment-emergent IRRs
 - Related treatment-emergent IRRs
- TEAEs by SOC and PT and worst grade (secondary endpoint)
- Related TEAEs by SOC and PT and worst grade (secondary endpoint)
- TEAEs leading to death by SOC and PT
- Related TEAEs leading to death by SOC and PT

15.2.2 Adverse Events Leading to Treatment Discontinuation

The frequency (number and percentage) of subjects with each of the following will be presented for TEAEs leading to permanent discontinuation (drug withdrawal), by dose level:

- TEAEs leading to discontinuation of avelumab by SOC and PT

The listing of all TEAEs leading to treatment discontinuation will also be provided with the relevant information.

15.3 Deaths, Other Serious Adverse Events, and Other Significant Adverse Events

15.3.1 Deaths

The frequency (number and percentage) of subjects who died, who died within 30 days after last dose of study treatment, and who died within 60 days after first dose of study treatment as well as

the primary reason for death, will be tabulated based on information from the “Death” and “Subject Status/Survival Follow-Up” eCRFs, by dose level.

- All Deaths
- Deaths within 30 days after last dose of study drug
- Deaths within 60 days after first dose of study drug
- Primary Reason for Death
 - Disease progression
 - Event related to Avelumab
 - Event not related to Avelumab
 - Unknown

In addition, date and cause of death will be provided in individual subject data listing together with selected dosing information (study treatment received, date of first / last administration, dose) and will include the following information:

- AEs with fatal outcome (list preferred terms of AEs with outcome=Fatal, as well as AEs of Grade 5),
- Flag for death within 30 days of last dose of study treatment.
- Flag for death within 60 days of first dose of study treatment

15.3.2 Serious Adverse Events

The frequency (number and percentage) of subjects with each of the following will be presented for treatment emergent SAEs by dose level:

- SAEs by SOC and PT
- Related SAEs by SOC and PT

A listing of all SAEs will also be provided with the relevant information with a flag for SAEs with onset outside of the on-treatment period.

15.3.3 Other Significant Adverse Events

An overall summary of treatment emergent irAEs table will include the frequency (number and percentage) of subjects with each of the following treatment emergent irAEs by dose level:

- irAEs
- Serious irAEs
- irAEs, Grade ≥ 3
- irAEs leading to permanent treatment discontinuation
- irAEs leading to death

- The frequency (number and percentage) of subjects with each of the following will be presented for treatment emergent irAEs, by dose level:
- irAEs by SOC and PT and worst toxicity grade

The listing of all irAEs will be provided with the relevant information, including whether there was a clear etiology for the event and whether a biopsy showed histopathology consistent with an immune-related event.

An overall summary of infusion related reactions (IRRs) table will include the frequency (number and percentage) of subjects with each of the following treatment emergent IRRs by dose level:

- IRRs
- Serious IRRs
- IRRs, Grade ≥ 3
- IRRs leading to permanent treatment discontinuation
- IRRs leading to death
- Timing related to first onset of IRR

The frequency (number and percentage) of subjects with each of the following will be presented for treatment emergent IRRs, by dose level:

- IRRs, by PT and worst toxicity grade

The listing of all IRRs will also be provided with the relevant information collected from the "Adverse Event Details" eCRF page.

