Subjects who start treatment and discontinue from the study on the same day may have two different sets of data collected on study day 1 (one during study and one in the End of Treatment (EOT) visit). Data reported at the EOT visit are not eligible for baseline selection.

If a scheduled pre-dose measurement actually occurred post-dose, then the corresponding measurement will be treated and analyzed similar to an unscheduled post-dose measurement.

Baseline for HR and QT/QTc assessments will be derived from the visit where both HR and QT are not missing. QTcF will be derived based on HR and QT.

Definition of study day:

Study day is defined relative to the date of start of treatment. Study day 1 defines the day of first administration with avelumab, the day before is defined as study day -1 (no study day 0 is defined).

Definition of on-treatment period:

The on-treatment period is defined as the time from the first dose of study treatment through minimum (30 days + last dose of study treatment, start day of new anti-cancer drug therapy - 1 day).

The date of new anti-cancer drug therapy after start date is derived as outlined in Section 12.1.

Definition of duration:

Duration will be calculated by the difference of start and stop date + 1 (e.g. survival time (days) = date of death - date of first dose of study drug + 1).

The time since an event (e.g. time since first diagnosis) will be calculated as reference date minus date of event.

Standard derivations and reporting conventions:

The following conversion factors will be used to convert days into months or years:

1 week = 7 days, 1 month = 30.4375 days, 1 year = 365.25 days.

Demographic and physical measurements:

- Age [years]:
 - (date of given informed consent - date of birth + 1) / 365.25
 - In case only year and month of birth are given: Age [years]: (year/month of given informed consent - year/month of birth) / 12
 - In case only year of birth is given: Age [years]: (year of given informed consent - year of birth)

The integer part of the calculated age will be used for reporting purposes.

- BMI (kg/m^2) = weight (kg)/[height (m)]².
- BSA (m^2) = ([height (cm) × weight (kg)] / 3600)^{0.5} (1)

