Immune-mediated rash, Immune-mediated colitis, Immune-mediated pneumonitis, Immune-mediated hepatitis, Immune-mediated nephritis and renal dysfunction, Immune-mediated endocrinopathies (Thyroid disorders: Hypothyroidism, Hyperthyroidism, and Thyroiditis), Immune-mediated endocrinopathies (Adrenal insufficiency, Immune-mediated endocrinopathies (Type 1 Diabetes Mellitus), Immune-mediated endocrinopathies (Pituitary dysfunction), Immune-mediated endocrinopathies (Hypogonadism), Other immune-mediated adverse events. Further details e.g. MeDDRA PT queries are regularly updated based on the current MeDRA version.

In order to standardize the MedDRA PT queries as much as possible, High Level Terms (HLT) and Standardized MedDRA Queries (SMQ) will be used whenever a choice, that is considered reflective of the events of interest, is available.

Level 2:

In a second level (medical review), the potential immune-mediated AEs identified from the search performed at Level 1, will be reviewed by qualified medical personnel to determine whether the AE meets the criteria (case definition) for an immune-mediated adverse reaction based on the following algorithm:

Table 10 Algorithm for immune-related adverse reactions

Criteria	Description
Onset	AE onset after 1st avelumab administration until up to 90 days after last dose
Duration	AE does not spontaneously resolve (i.e., without corticosteroids/ immunosuppressant treatment) within 7 days after onset
Immunosuppressive therapy	AE treated with corticosteroid or other immunosuppressant therapy. For endocrinopathies only: AE required hormone replacement* and /or (corticosteroid or other immunosuppressive therapy)
Etiology	No other clear etiology or Histopathology/biopsy consistent with immune-mediated event
All criteria listed in the left column need to be fulfilled for an event to meet the case definition of immune-mediated reaction.	
*Hormone replacement will be evaluated for specific endocrinopathy disorders only as follows: 
 • Thyroid disorders (HLT): Thyroid therapy (ATC codes (H03A, H03B)) • Diabetes mellitus (including hyperglycaemia): Insulin (ATC code A10A) 	

Infusion related reactions are identified based on a list of MedDRA PTs and criteria on the timely relationship according to Table 11.

Table 11 Criteria for infusion related reactions

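### The irAE frequency tables stop no later than 30 days after the last dose, while the SAP's own irAE case definition runs to 90 days; a companion 90-day count would be a cheap improvement

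*SAP*

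**What the plan says.** **Case definition.** SAP 15.2 states: "For the final analysis, immune related adverse events according to case definition classified by medical review". It points to Table 10 in Appendix I, whose onset criterion is "AE onset after 1st avelumab administration until up to 90 days after last dose".

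**Reporting window.** SAP 15.2 introduces irAEs under the sentence "The following categories of TEAEs are defined for reporting" and adds: "All analyses described in Section 15.2 and 15.3 will be based on TEAEs if not otherwise specified". SAP 9 ends the on-treatment period at the minimum of "30 days + last dose of study treatment, start day of new anti-cancer drug therapy - 1 day".

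**Outputs that give an irAE frequency.** There are three:
- the row "Treatment-emergent irAEs" in the overall AE summary (SAP 15.2.1);
- the irAE overview in SAP 15.3.3: "An overall summary of treatment emergent irAEs table will include the frequency (number and percentage) of subjects" in each irAE category, by dose level;
- the 15.3.3 table by system organ class (SOC), preferred term (PT) and worst grade, also limited to treatment-emergent irAEs.

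**Listings.** SAP 15.3.3 adds: "The listing of all irAEs will be provided with the relevant information". SAP 15.2 says AE listings cover all AEs and flag those outside the on-treatment period.

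**Protocol.** Section 8.5.3.3 plans summaries of treatment-emergent AEs of special interest. The definition of such events (7.4.1.1) and the endpoint (8.3.2) set no treatment-emergent limit. Sections 7.1.4 and 7.4.1.3 extend safety collection to the 90-day telephone call.

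**The concern.** The protocol asks sites to document SAEs and treatment-related non-serious AEs for 90 days after the last dose, and the SAP has medical reviewers judge possible irAEs on the same horizon. The frequency tables then use a shorter window. An event can be collected, reviewed and confirmed as immune-related, and still add nothing to any irAE count or percentage.

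AEs of special interest are a secondary safety endpoint. Protocol 6.5.4 itself expects irAEs to appear only after weeks of treatment, so onset after a short course has ended is foreseeable. A reader who wants the frequency on the SAP's own definition would have to recount it from listings.

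**Working it through.** The plan states no figure on this point, so there is none to reproduce. The check compares two windows and then works out what one uncounted subject is worth.

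**1. Windows.** Let L be the date of the last dose.
- Case definition (Table 10): first dose to L + 90.
- Irrespective of the case definition, treatment-emergent events (SAP 9): first dose to min(L + 30, start of new anti-cancer drug - 1).
- Gap with no new drug by day 30: 90 - 30 = 60 days (L + 31 to L + 90), and 60/90 = 67% of the post-dose calendar days.
- New drug on L + 15: the on-treatment period ends at L + 14 and the gap is 90 - 14 = 76 days.
- New drug on L + 1: the gap is 90 - 0 = 90 days.

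Sixty days is therefore the minimum gap.

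**2. Share of all irAE-eligible time.** The 67% covers post-dose days only. Assume on-schedule dosing every 2 weeks and no new drug by day 30. With d doses, the last dose is on study day 1 + 14(d - 1), and the eligible time is that day number plus 90.

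| Doses (assumed) | Eligible days | Share in the 60-day gap |
|---|---|---|
| 2 | 15 + 90 = 105 | 60/105 = 57% |
| 4 | 43 + 90 = 133 | 60/133 = 45% |
| 12 | 155 + 90 = 245 | 60/245 = 24% |

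These are shares of time, not of events.

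**3. Where a late confirmed irAE goes.**
- Listing of all irAEs: included.
- AE and SAE listings: included, with a flag.
- Deaths table (SAP 15.3.1), if fatal: included under all deaths.
- The three irAE frequency outputs: not included.

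**4. Exception through date imputation.** SAP 9 replaces a completely missing AE onset date by the start of treatment. In most other cases a missing day becomes the 1st of the month. Example with assumed dates: last dose 10 March, so L + 30 is 9 April. A true onset on 20 April recorded only as April is imputed to 1 April and counted. Imputation can therefore pull a late event into the tables.

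**5. Effect per subject.** Protocol 5.1.1 plans 12 to 36 Phase I subjects. If k treated subjects have a late irAE as their only confirmed irAE, the overall frequency falls by k/n.
- k = 1: 1/36 = 2.8 to 1/12 = 8.3 percentage points.
- k = 2: 2/36 = 5.6 to 2/12 = 16.7 points.

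Phase I completes at a dose level with at least 12 DLT-evaluable subjects (protocol 5.1.1.1.6). At that level the effect is at most 8.3 points for each affected subject. The figure does not cap the total. The documents give no value for k.

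**The case against.** The strongest reply is that this is a planned choice. Table 10 decides whether an event is immune-mediated; the tables apply a separate reporting window. The protocol and SAP agree on treatment-emergent summaries, and nothing promises a 90-day frequency. Late events remain visible in listings, and with 12 to 36 subjects a recount is easy. Ascertainment is also weaker after day 30:
- No routine hematology, chemistry, thyroid tests or physical examinations are scheduled between the 30-day visit and the 90-day call.
- Unrelated non-serious AEs may go unrecorded.
- Next-line therapy confounds attribution.

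Much of this stands. A reader might infer that the SAP contradicts the protocol, or that the tables are wrong. Protocol 8.5.3.3 rules out both. A reader might also infer from the SAP's modification history, which records dropping a separate listing of irAEs outside the on-treatment period, that late irAEs vanish from the report. The current 15.3.3 lists all irAEs, so they do not. Nor does 67% mean that two-thirds of irAEs are missed; it is a share of calendar days.

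What remains is that a listing supplies no count, percentage or worst-grade summary for events the review has already confirmed. Incomplete late data call for a footnote and a separate presentation. They are not a reason to leave confirmed events uncounted.

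**Conclusion.** The point holds as a cheap improvement, not as the correction of an error. Relative to the SAP's own case definition, the treatment-emergent tables can match or understate the irAE frequency. They omit at least 60 of the 90 post-dose days, apart from late events whose onset dates are imputed into the window. The cost is 2.8 to 8.3 percentage points overall for each subject whose only confirmed irAE is late. That range assumes the treated number falls within the planned 12 to 36. The number of such subjects is unknown and may be zero, so no actual understatement is shown. DLTs and Grade 3 or higher TEAEs, the primary endpoints, are unaffected.

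Two data-collection ambiguities affect how well a 90-day count could be made, but they do not cause the mismatch:
- Protocol Table 1 footnote j records concomitant medication through the Safety Follow-up Visit, whereas 6.5.2 says 90 days after the last dose. Table 10 needs data on steroid or immunosuppressant treatment, or hormone replacement for endocrinopathies.
- Footnote k ends non-serious AE reporting when new therapy starts, yet also provides for related AEs on days 31 to 90. Whether that provision, or footnote b, still applies after new therapy is unclear.

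**What to change.** Keep the three treatment-emergent outputs. In SAP 15.3.3 add rows or a companion table (overview, and SOC, PT and worst grade) counting every medically confirmed irAE with onset from first dose to 90 days after the last dose. Flag onsets after the start of new anti-cancer therapy. Footnote that days 31 to 90 are less completely ascertained.

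As a separate clarification, reconcile footnote j with protocol 6.5.2, settle under footnotes b and k whether related non-serious AEs are recorded after new therapy, and state in the SAP which rules the collected data follow.

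The cost is a little programming, since the medical review already makes the confirmations. The drawback is that late data are incomplete and confounded by next-line therapy, so the 90-day count should sit beside the treatment-emergent tables and not replace them.

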15.4 Clinical Laboratory Evaluation

15.4.1 Hematology and Chemistry Parameters

Treatment emergent laboratory assessments are any sample collected after the first dose of study treatment administration and within 30 days from the last study treatment administration.

Laboratory results will be classified according to the NCI-CTCAE criteria version 4.03. Non-numerical qualifiers (with the exception of fasting flags) will not be taken into consideration in the derivation of CTCAE criteria (e.g., hypokalemia Grade 1 and Grade 2 are only distinguished by a non-numerical qualifier and therefore Grade 2 will not be derived). Additional laboratory results that are not part of NCI-CTCAE will be presented according to the categories: below normal limit, within normal limits and above normal limit (according to the laboratory normal ranges).

The worst on-treatment grade (i.e. on or after first study treatment administration and within 30 days after last study treatment administration) will be summarized considering only subjects with post baseline laboratory samples: Laboratory tests by NCI-CTCAE grade (0, 1, 2, 3, 4, any).

Abnormalities classified according to NCI-CTCAE toxicity grading version 4.03 are a secondary endpoint for this study and will be described by dose level using the worst grade. For those parameters which are graded with two toxicities such as potassium (hypokalemia/hyperkalemia), the toxicities will be summarized separately. Low direction toxicity (e.g., hypokalemia) grades at baseline and post baseline will be set to 0 when the variables are derived for summarizing high direction toxicity (e.g., hyperkalemia), and vice versa.

For **WBC differential counts** (total neutrophil [including bands], lymphocyte, monocyte, eosinophil, and basophil counts), the absolute value will be used when reported. When only percentages are available (this is mainly important for neutrophils and lymphocytes, because the CTCAE grading is based on the absolute counts), the absolute value is derived as follows:

$$\text{Derived differential absolute count} = (\text{WBC count}) * (\text{Differential \%value} / 100)$$

If the range for the differential absolute count is not available (only range for value in % is available) then Grade 1 will be attributed to as follows:

- Lymphocyte count decreased:
 - derived absolute count does not meet Grade 2-4 criteria, and
 - % value < % LLN value, and
 - derived absolute count $\geq 800/\text{mm}^3$
- Neutrophil count decreased
 - derived absolute count does not meet Grade 2-4 criteria, and
 - % value < % LLN value, and
 - derived absolute count $\geq 1500/\text{mm}^3$

For **calcium**, CTCAE grading is based on Corrected Calcium and Ionized Calcium (CALCIO), if available. Corrected Calcium is calculated from Albumin and Calcium as follows

$$\text{Corrected Calcium (mmol/L)} = \text{measured total Calcium (mmol/L)} + 0.02 (40 - \text{serum albumin [g/L]}).$$

Liver function tests: Alanine aminotransferase (ALT), aspartate aminotransferase (AST), and total bilirubin (TBILI) are used to assess possible drug induced liver toxicity. The ratios of test result over upper limit of normal (ULN) will be calculated and classified for these three parameters during the on-treatment period.

A listing of all TBILI, ALT, AST and ALP values for subjects with a post-baseline TBILI $\geq 2 \times \text{ULN}$, ALT $\geq 3 \times \text{ULN}$ or AST $\geq 3 \times \text{ULN}$ will be provided.

Parameters with NCI-CTCAE grades available (secondary endpoint):

The laboratory toxicities will be tabulated using descriptive statistics (number of subjects and percentages) during the on-treatment period. The denominator to calculate percentages for each laboratory parameter is the number of subjects evaluable for CTCAE grading (i.e., those subjects for whom a Grade 0, 1, 2, 3, or 4 can be derived).

- The summary of laboratory parameters by CTCAE grade table will include number and percentage of subjects with Grade 1, 2, 3, 4, 3/4, and any grade (1 to 4) laboratory abnormalities during the on-treatment period – (worst case)

The above analyses apply to hematology and chemistry evaluations which can be graded per CTCAE, i.e.:

- Hematology:
Hemoglobin (HB), Leukocytes (white blood cell decreased), Lymphocytes (lymphocyte count increased/decreased), Neutrophils / Absolute Neutrophils Count (ANC) (neutrophil count decreased), Platelet Count (PLT) (platelet count decreased).
- Serum Chemistry:
Albumin (hypoalbuminemia), Alkaline Phosphatase (alkaline phosphatase increased), Alanine Aminotransferase (ALT) (ALT increased), Amylase (serum amylase increased), Aspartate Aminotransferase (AST) (AST increased), Total Bilirubin (blood bilitubin increased, Cholesterol (cholesterol high), Creatinine (creatinine increased), Creatine Kinase (CPK increased), Potassium (hypokalemia/ hyperkalemia), Sodium (hyponatremia/ hypernatremia), Magnesium (hypomagnesemia/hypermagnesemia), Calcium (hypocalcemia/ hypercalcemia), Glucose (hypoglycemia/hyperglycemia), Gamma Glutamyl Transferase (GGT) (GGT increased), Lipase (lipase increased), Phosphates (hypophosphatemia), Triglycerides (hypertriglyceridemia).

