#### 5.3.1 Inclusion Criteria

Subject eligibility should be reviewed and documented by the Investigator or delegate of the Investigator's study team before subjects are included in the study.

For inclusion in the trial, all of the following inclusion criteria must be fulfilled:

1. Signed written informed consent form (ICF) before any trial-related procedure is undertaken that is not part of the standard patient management. The signed ICF indicates that the minor subject's parent(s)/legal guardian(s) have been informed of all pertinent aspects of the study, based on local regulations. Subjects also must provide assent when age appropriate and per local regulations.
2. Male and female subjects 0 to < 18 years of age at the time of first treatment dose.
3. Availability of formalin-fixed paraffin-embedded (FFPE) block containing tumor tissue or a minimum of 10 (preferably 25) unstained tumor slides (cut within 1 week) suitable for PD-L1 expression assessment, from a recently obtained (within 6 months) biopsy from a non-irradiated area. If tissue is unavailable in block or slides, a mandatory tumor biopsy must be performed prior to avelumab treatment for subjects in Phase II.
4. Subjects with histologically or cytologically proven diagnosis of malignant solid tumor (including CNS tumors) or lymphoma in Phase I, or specified tumor types in Phase II with measurable disease at Baseline (at least 1 unidimensional, radiographically measurable lesion based on RECIST v1.1).
5. Confirmed progression on or refractory to standard therapy, or no standard therapy available.
6. Lansky performance status  $\geq 50\%$  for subjects  $\leq 16$  years of age, or Karnofsky scale  $\geq 50\%$  for subjects  $> 16$  years of age.
7. Adequate bone marrow function, including:
  - a. Absolute neutrophil count  $\geq 1,000/\text{mm}^3$  or  $\geq 1 \times 10^9/\text{L}$  at least 5 days following the last dose of granulocyte colony stimulating factor
  - b. Platelets  $\geq 50,000/\text{mm}^3$  or  $\geq 50 \times 10^9/\text{L}$
  - c. Hemoglobin  $\geq 8$  g/dL (may have been transfused).
8. Adequate hepatic function, defined by:
  - a. a total serum bilirubin level  $\leq 1.5 \times$  the upper limit of normal range (ULN)
  - b. an aspartate aminotransferase (AST) level  $\leq 3.0 \times$  ULN
  - c. an alanine aminotransferase (ALT) level  $\leq 3.0 \times$  ULN or, for subjects with documented metastatic disease to the liver, AST and ALT levels  $\leq 5 \times$  ULN.

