#### Laboratory Values

Laboratory results will be classified by grade according to NCI-CTCAE v4.03. The worst on-treatment grades for chemistry and hematology laboratory results will be summarized. Shifts in toxicity grading from Baseline to highest grade during the on-treatment period will be displayed. For laboratory tests without an NCI-CTCAE grade definition, results will be presented categorically (eg, below, within, or above normal limits).

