	To evaluate programmed death ligand (PD-L1) expression; tumor infiltrating T-cell activity; T-cell population; and T-cell, B-cell and NK-cell numbers in tumor tissue at Baseline and at confirmed progression (if tumor tissue is obtained)	
Secondary Endpoint:
 
 Assessment of tumor PD-L1 expression; tumor-infiltrating T-cell activity; T-cell population; and T-cell, B-cell, and NK-cell numbers at Baseline and at confirmed progression (if tumor tissue is obtained) 	16.3 Biomarkers

	Objective	Endpoint	IAP section
	To measure changes in vaccination-related antibody concentrations (diphtheria, tetanus, and pneumococcal conjugate)	Secondary Endpoint: 
Vaccination-related antibody concentrations	16.4 Vaccination-related antibody concentrations

6 Overview of Planned Analyses

This document covers the avelumab standards for analyses of efficacy and safety. There are no interim analyses for efficacy planned for this trial, but ad hoc interim analyses may be conducted if necessary. There will be periodic safety review by the safety monitoring committee (SMC). The SMC will be responsible for reviewing the safety data and output containing the following information:

- The number and proportion of subjects in the DLT Analysis Set who experienced a DLT during the DLT evaluation period (first two cycles or 28 days of study treatment)
- The number and proportion of TEAEs experienced by subjects in the DLT Analysis Set during the DLT evaluation period
- The number and proportion of TEAEs \geq Grade 3 experienced by subjects in the DLT Analysis Set during the DLT evaluation period.

The SMC will also review patient profiles.

All final, planned analyses identified in the Clinical Trial Protocol and in this IAP will be performed after the last subject has completed his or her end of treatment visit or has been transferred off the trial, and all study data is in-house, all data queries are resolved, and the database is locked.

Statistical analyses will be performed using cleaned eCRF data as well as external data including laboratory data.

7 Changes to the Planned Analyses in the Clinical Trial Protocol

The statistical methods specified in this document are in accordance with protocol version 2.0 (dated 15 September 2017).

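### The SAP drops the protocol's baseline-to-worst-grade laboratory shift table without declaring it, so no summary table separates abnormalities present at entry from new or worsened ones

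*SAP*

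**What the plan says.** Protocol 8.5.3.3 (Laboratory Values) asks for a summary of worst on-treatment grades and then adds a second display: "Shifts in toxicity grading from Baseline to highest grade during the on-treatment period will be displayed".

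SAP 15.4.1 specifies the first display only. Its introduction reads "The laboratory toxicities will be tabulated using descriptive statistics (number of subjects and percentages) during the on-treatment period", and the table gives the "number and percentage of subjects with Grade 1, 2, 3, 4, 3/4, and any grade (1 to 4) laboratory abnormalities during the on-treatment period". Each subject is counted at the highest grade reached. Three further rules fix what is counted:

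- Emergence is a matter of timing: "Treatment emergent laboratory assessments are any sample collected after the first dose of study treatment administration". The window closes 30 days after the last dose.
- The worst grade "will be summarized considering only subjects with post baseline laboratory samples".
- For percentages, "The denominator to calculate percentages for each laboratory parameter is the number of subjects evaluable for CTCAE grading".

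None of these uses the baseline grade. The SAP's modification history (Section 3, version 2.0) records that the shift-to-worst-grade table was taken out. Section 7, where departures from the protocol belong, lists changes to the PK, immunogenicity and biomarker analysis sets but not this one. It opens with "The statistical methods specified in this document are in accordance with protocol version 2.0 (dated 15 September 2017").

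**The concern.** The trial has one arm, so each child's own baseline is the only comparator for laboratory change. Graded laboratory abnormalities are a secondary endpoint under the primary safety objective and are reported by dose level. A worst-grade table with no shift table beside it cannot tell a reader whether a Grade 2 ALT arose on avelumab or came in with the child. The SAP's introduction calls the counts toxicities, which invites the first interpretation.

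The clinical adverse event rule in SAP 15.2 does require first onset or worsening on treatment. One report would therefore use two meanings of treatment-emergent, one of them blind to baseline. With cohorts of 3 to 6 children, a chance difference between dose levels in entry abnormalities could pass for a difference in tolerability.

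**Working it through.** The plan states no figure on this point, so there is nothing to reproduce. The check compares texts, followed by an illustration of size.

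**1. Can a child enter with a graded value?** Entry limits are from Protocol 5.3.1. Liver bands are from the hepatic rows of Protocol Table 5. The neutrophil condition is from SAP 15.4.1.

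| Parameter | Entry limit | Band printed in the documents | Possible at entry |
|---|---|---|---|
| AST/ALT | up to 3 x ULN | Grade 1: above ULN to 3 x ULN | Grade 1 |
| AST/ALT, liver metastases | up to 5 x ULN | Grade 2: above 3 to 5 x ULN | Grade 2 |
| Bilirubin | up to 1.5 x ULN | Grade 1: above ULN to 1.5 x ULN | Grade 1 |
| Bilirubin, Gilbert disease | below 3 x ULN | Grade 2: above 1.5 to 3 x ULN | Grade 2 |
| Neutrophils | from 1,000/mm3 | Grade 1 rule for derived counts needs at least 1,500/mm3 | 1,000 to 1,499/mm3 is below the Grade 1 floor |

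Exclusion criterion 10 (Protocol 5.3.2) bars persisting prior-therapy toxicity only above Grade 2, so Grade 1 or 2 may be present at entry.

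**2. What happens to such a child if nothing changes?** Any post-baseline sample at the same value is on treatment and graded 1 or higher. The child enters the numerator at that grade, and the denominator takes every gradable subject. No condition removes the child from either.

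**3. Does another summary make the distinction?**

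- Under Protocol 7.4.1.1, a laboratory abnormality is an adverse event only if it has clinical signs or symptoms, leads to discontinuation, or is judged medically important. The TEAE tables cover only those.
- The liver listing in SAP 15.4.1 is triggered by post-baseline ALT or AST at or above 3 x ULN, a level that a child with liver metastases may have at entry.
- SAP 15.4.2 provides listings of all results and of CTCAE grades. The information therefore exists by subject, but in no summary table.

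**4. How large could it be?** One carried-over child adds 1/n to the any-grade share of a dose level with n gradable subjects: 1/6 = 17 percentage points, 1/12 = 8.3, 1/36 = 2.8.

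For a parameter as a whole, let b be the share abnormal at baseline, s the chance that such a child has at least one abnormal on-treatment sample, and w the share truly new or worsened. Taking w as equal in both groups, and any worsening among the baseline-abnormal as already inside s, the reported share is

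R = b x s + (1 - b) x w.

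All three inputs are assumptions; none is in the documents. With w = 10%:

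| b | R at s = 0.8 | R at s = 1.0 | New or worsened |
|---|---|---|---|
| 10% | 0.08 + 0.09 = 17% | 0.10 + 0.09 = 19% | 10% |
| 30% | 0.24 + 0.07 = 31% | 0.30 + 0.07 = 37% | 10% |
| 50% | 0.40 + 0.05 = 45% | 0.50 + 0.05 = 55% | 10% |

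At b = 30% and s = 1.0 this is 12 x 0.37 = 4.4 against 12 x 0.10 = 1.2 subjects, or 36 x 0.37 = 13.3 against 3.6. With w = 0 the table would still show b x s, from 0.1 x 0.8 = 8% to 0.5 x 1.0 = 50%.

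**The case against.** The strongest reply is that the worst-grade table is what the protocol asks for. Protocol 8.5.3.3 requires that summary with no baseline condition, and the endpoint is worded as incidence of graded abnormalities, not of new or worsened ones. This stands. A reader might infer that the table is itself an error to be replaced by a count of worsened grades. The documents do not support that: the table should stay, and what is missing is its companion.

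Second, the removal was not hidden. The modification history records it and gives the background: monotherapy evaluation ended after Phase I and outputs were cut to the needs of Phase I reporting. This also stands, but a version log compares two SAP versions. It does not replace a declaration against the protocol in Section 7.

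Third, the primary endpoints are protected. TEAEs need onset or worsening on treatment, DLTs follow their own definition and SMC assessment, and no decision rule uses the laboratory table. This stands and limits the consequence to a descriptive secondary output.

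Fourth, with 12 to 36 subjects a reader can work from the listings. That is possible, but it leaves each reader to build the table that the protocol promised.

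**Conclusion.** The point holds as an undeclared departure that removes the only planned laboratory summary relating on-treatment grade to baseline. Unchanged entry abnormalities are counted on treatment. For AST/ALT and bilirubin the entry limits stop at Grade 2, so carry-over falls in the Grade 1, Grade 2 and any-grade columns. For neutrophils the bands beyond Grade 1 are not printed, but the exclusion of prior-therapy toxicity above Grade 2 points the same way.

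Two stronger readings are tempting and not supported:

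- That Grade 3/4 counts are materially inflated. For the capped parameters the entry limits work against this. For parameters with no entry limit, such as lymphocytes or lipase, the documents give nothing from which to judge.
- That a large, known fraction of hemoglobin or platelet counts is carry-over. The entry limits are 8 g/dL ("may have been transfused") and 50,000/mm3, but the documents print neither the grade bands for these parameters nor any baseline prevalence.

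The size is therefore unknown. The ranges above show how the mechanism behaves under assumed inputs and are not estimates for this trial.

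**What to change.** 1. Keep the worst-grade table, and title it as worst on-treatment grade regardless of baseline.
2. Restore the protocol's shift table, baseline grade by worst on-treatment grade, for the parameters already graded in SAP 15.4.1.
3. Give missing baseline its own row. Setting it to Grade 0 would count an unrecorded pre-existing abnormality as new, which is the same misclassification.
4. If the sponsor prefers not to restore the table, declare and justify its omission in Section 7. That settles the documentation but not the gap in reporting.

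The cost is small: SAP 15.4.1 already refers to grades at baseline and post baseline, so this is one table. The downside is somewhat more output than the reduced Phase I report intended. A shift table also shows movement, not cause: a hemoglobin falling back after a pre-entry transfusion would appear as worsening, and a footnote should say so.
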